#### Box 2: Secondary outcome measures

Hair cortisol levels	Hair cortisol reflect cumulative secretion of cortisol within the hair growth period, with high levels indicative of chronic or sustained stress.  We will obtain hair samples from providers who have enough hair (at least 2cm long) and willing to provide hair samples. Hair samples will then be processed to obtain cortisol levels. There are no specified cut-offs for cortisol levels, but, on average, higher cortisol levels indicate higher stress.
Hair rate variability	HRV is a measure of the beat-to-beat interval between consecutive heart beats to estimate cardiac vagal tone.  HRV will be measured using the CorSense finger monitor by Elite HRV,  and the natural log of the root mean square of successive differences in RR intervals (LnRMSSD) calculated.  The LnRMSSD reflect parasympathetic nervous system activity. Higher LnRMSSD is thus more adaptive and associated with relaxation and calm states, while low levels are associated with anxiety, high stress, and burnout. 
IAT	Two situationally specific vignettes assessing providers' perceptions of women's PCMC expectations and behaviors based on SES.  One vignette describes a woman with low SES and the other vignette a high SES woman; vignettes were read in counter-balanced orders to providers and followed by 8-questions assessing providers' perceptions of the woman's expectations for introductions, consenting, companionship, potential to cooperate, understand explanations, and exaggerate pain; and provider behavior needed to convey seriousness and gain patient cooperation. The vignettes and questions were informed by measurement of explicit bias in prior literature  and prior research in this setting  . Response options

	range from strongly disagree to strongly agree on a 4-point scale. Summative scores are created after recoding all responses to the same direction; higher scores indicate higher bias towards the woman in the vignette. Scores range from 0 to 27. Cronbach alpha for the 8 items in the study sample at baseline was 0.70 for the low SES vignette and 0.80 for the high SES vignette.
Explicit bias score.	Situationally specific vignettes assessing providers' perceptions of women's PCMC expectations and behaviors based on SES will be used to measure explicit bias  . One vignette describes a woman with low SES and the other vignette a high SES woman; vignettes were read in counter-balanced orders to providers and followed by 8-questions assessing providers' perceptions of the woman's expectations for introductions, consenting, companionship, potential to cooperate, understand explanations, and exaggerate pain; and provider behavior needed to convey seriousness and gain patient cooperation. The vignettes and questions were informed by measurement of explicit bias in prior literature  and prior research in this setting  . Response options range from strongly disagree to strongly agree on a 4-point scale. Summative scores are created after recoding all responses to the same direction; higher scores indicate higher bias towards the woman in the vignette. Scores range from 0 to 27..

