#### *Implicit association test (IAT)*

Following each interview, providers will be asked to fill out the IAT. The IAT is a test that has been validated to measure implicit biases, and has been used in many different settings. It measures the strength of associations between concepts (e.g., black people, poor people) and evaluations (e.g., good, bad) or stereotypes (e.g., athletic, clumsy). The main idea is that making a response is easier when closely related items share the same response key. When doing an IAT people are asked to quickly sort words into categories that are on the left and right hand side of the computer screen by pressing the “e” key if the word belongs to the category on the left and the “i” key if the word belongs to the category on the right. In this study, we will be using the IAT to examine evaluations and stereotypes based on people’s socioeconomic status, which we developed as part of CPIPE 1. The IAT is programmed with a software called Inquisit Lab that stores the data generated together with a respondent ID which is entered before the initiation of the test. A spreadsheet containing the HRV by ID numbers is then downloaded from the app and merged with the survey data for analysis.

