#### b. Secondary outcomes

We also have four secondary outcomes: 1) Hair cortisol levels, 2) Hair rate variability, 3) IAT, and 4) explicit bias score. A brief description of these outcome variables are provided in Box 2.

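### The SAP defines the IAT secondary outcome with the explicit-bias vignettes, and neither document says how the IAT is scored

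*Combined protocol and SAP*

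**What the plan says.** Section b (Secondary outcomes) of the SAP names four outcomes: "1) Hair cortisol levels, 2) Hair rate variability, 3) IAT, and 4) explicit bias score". Box 2 is meant to define each of them.

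The Box 2 row labelled IAT begins "Two situationally specific vignettes assessing". It describes one vignette about a woman of low socioeconomic status (SES) and one about a woman of high SES, each followed by eight questions. It says of their origin: "The vignettes and questions were informed by measurement of explicit bias in prior literature". It also reports a result already obtained: "Cronbach alpha for the 8 items in the study sample at baseline was 0.70 for the low SES vignette", with 0.80 for the high-SES vignette.

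The next row, Explicit bias score, describes vignettes that "based on SES will be used to measure explicit bias", with the same questions. On scoring it says "Response options range from strongly disagree to strongly agree on a 4-point scale" and "higher scores indicate higher bias towards the woman in the vignette. Scores range from 0 to 27". The IAT row gives the same response scale and range.

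The protocol separates the two. Its section on data collection procedures and measures names the IAT and vignettes as two tools. Its Table 2 puts IAT scores under Attitudes and vignettes under Behavior. Its section Implicit association test (IAT) describes a speeded key-press sorting task about SES, programmed in Inquisit Lab, with data stored by respondent ID. On timing it says "Following each interview, providers will be asked to fill out the IAT".

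**The concern.** An outcome called IAT should be measured by the IAT. As Box 2 stands, outcomes 3 and 4 are the same variable under two names, and no SAP row describes the sorting task that the protocol plans to run.

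Two things are at stake. An analyst who follows the SAP to the letter would report explicit-bias results under an implicit-bias label. An analyst who recognises the slip and uses the real IAT data would find no rule for turning them into a score, so the summary, its direction and any exclusions could be settled after the data are seen.

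This matters because unconscious bias is one of the two targets of the intervention, and the IAT is the only listed outcome that measures implicit bias itself. The bias measure among the primary outcomes is a 17-question knowledge and attitude assessment.

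**Working it through.** **1. Compare the two Box 2 rows.** Word alignment in order, with citation numbers removed:

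| | Words | Matched in order | Unmatched |
|---|---|---|---|
| IAT row | 162 | 135 (135/162 = 83%) | 27: the opening word (1) and the Cronbach alpha sentence (26) |
| Explicit bias row | 142 | 135 (135/142 = 95%) | 7: the phrase stating that the vignettes measure explicit bias |

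The rows differ at the opening, and only one reports alphas. They are therefore two separately written rows, not one row read twice from the PDF.

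**2. Count instruments.** Box 2 defines hair cortisol, heart rate variability (HRV), vignettes and vignettes again: 3 instruments for 4 outcomes. None of its rows describes the sorting task.

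**3. Look for an IAT scoring rule elsewhere.**
- The protocol's IAT section gives the principle (sorting is easier when related items share a key), the SES topic, the software and storage by ID.
- The only sentence there on exporting data names HRV. It is the same 22-word sentence that closes the protocol's HRV section, so it says nothing about the IAT.
- Protocol Table 2 mentions IAT scores without defining them. The protocol's analysis plan is generic: regression and difference in differences (DID).
- Of the three elements needed (summary score, direction, rule for invalid runs), 0 of 3 are stated for the IAT. Each of the other seven primary and secondary outcomes has a description of its own measure and a direction.

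**4. Count the results affected.** The SAP gives each secondary outcome a within-group Wilcoxon signed-rank test in each of two arms and one DID estimate.
- One score per outcome: 4 × (2 + 1) = 12 results, of which 3 would be vignette results labelled IAT.
- Low- and high-SES vignettes analysed separately: cortisol 3 + HRV 3 + IAT row 6 + explicit row 6 = 18 results, of which 6 would carry the IAT label.

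The SAP does not say which of these applies.

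**5. Check the printed range of 0 to 27.** A sum of k items runs from k × lowest code to k × highest code.
- 8 items coded 0–3: 0 to 24.
- 8 items coded 1–4: 8 to 32.
- Both vignettes together, 16 items: 0 to 48, or 16 to 64.
- 9 items coded 0–3: 0 to 27.

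Of these, only nine items coded 0–3 reproduce the printed range. The text gives eight items, and the topics it lists also number eight (six perceptions and two behaviours).

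**The case against.** The strongest reply is that this is a paste error that readers will catch. The protocol sits in the same combined document and describes the real IAT, and the SAP lists the two outcomes separately, so few analysts would report vignettes as the IAT. That is probably right about the label. It does not supply the missing score: once the wrong text is removed, the IAT row is empty.

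A second reply is that a rule may exist outside these documents. The SES version of the test was developed in the first phase of the project (CPIPE1), and the protocol cites general IAT references. This cannot be excluded. The point is therefore limited to what the documents state, and they neither name nor adopt a scoring method.

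Third, the evidence that scoring could be chosen late is modest. The baseline alphas belong to the vignette items, not to the IAT. They show that baseline vignette data had been analysed when this SAP text was written; they do not show that anyone had looked at IAT data. This limit stands. Because the IAT is taken after each interview, baseline IAT data could have existed by then, so a late choice is possible. Nothing shows that it happened.

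Fourth, the stakes are limited. These are secondary outcomes in a pilot that the SAP itself regards as probably too small for formal testing, and the protocol expects that unconscious bias may not shift within six months. This stands too, and it lowers the importance of the point without removing it.

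**Conclusion.** The concern holds. The Box 2 definition of the IAT outcome is wrong as written: it describes the explicit-bias vignettes and conflicts with the protocol. One instrument covers 2 of 4 secondary outcomes, and the real IAT has no stated score, direction or rule for invalid runs in either document. The count of 3 mislabelled results out of 12 assumes one score per outcome; it becomes 6 out of 18 if the two vignettes are analysed separately.

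The primary outcomes and the sample size are not touched. Whether a scoring rule was carried over from CPIPE1 cannot be seen here. This should be fixed before the secondary outcomes are analysed. The mismatch between the 0–27 range and eight items is a smaller error in the vignette score.

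**What to change.** - **Box 2, IAT row:** replace the text with the SES sorting task from the protocol's IAT section. State the summary score with its formula, what a higher value means, which runs are invalid and how they are handled, and the date on which the rule was fixed. If a CPIPE1 rule is being used, cite it with its date.
- **Box 2, Explicit bias score row:** keep the vignettes only here and move the Cronbach alpha sentence into this row.
- **Vignette score (minor):** reconcile the range with eight four-point items, and say whether the low- and high-SES scores enter the DID separately or combined.
- **Protocol, IAT section (clerical):** correct the export sentence so that it names the IAT data.

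The cost is text only, with no new data and no change to primary outcomes or sample size. The drawback is that, unless an earlier rule exists, the IAT rule would be fixed after baseline collection, which is why it should carry its date. If endline data had also been seen by then, the IAT result should be labelled as scored post hoc.

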Bias is the negative evaluation of one group relative to another. It can be explicit/conscious or implicit/unconscious. UB operates at an unintentional level and so does not require a person to endorse it or devote attention to its expression. Instead, it can be activated quickly and unknowingly by situational cues such as a person's skin color, accent, or low status clothes. UB is prevalent in every society, although the type of biases may differ in different contexts. In the US, where racial bias has been extensively studied, greater pro-White bias among physicians is associated with disparities in quality of care, with lower likelihood of prescribing thrombolytics for Black compared to White patients with acute coronary syndrome; lower inclination to prescribe pain medications for Black versus White children; and poorer ratings of interpersonal care among Black versus White patients. Our work in Kenya supports the critical role of UB in PCMHC disparities by SES, age, tribe, and HIV status.

The way people are treated in healthcare settings is a reflection of the broader societal norms and behaviors. In societies where gender-based violence, disrespect of the poor, tribalism, and differential treatment based on SES are normative—and providers are higher in the social hierarchy than patients—providers are more likely to (unconsciously) treat patients with disrespect. Providers are, however, more likely to be conscious of their actions and to treat patients with respect when they meet someone who challenges their social standing. Low SES women hardly challenge how they are treated, reinforcing mistreatment towards them. This supports the idea that disrespect thrives in a culture that tolerates disrespect, and individual biases may reinforce patterns of abuse. Addressing biases against marginalized groups is especially important in Migori County given the poor status of women, the high rates of teenage pregnancy, and the high prevalence of HIV in the area.

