**Table 1: Intervention strategies**

**1. Training**

We will develop a training for providers that addresses the following topics

- Stress & positive coping mechanisms
- Unconscious bias awareness and mitigation
- Person-centered maternity care
- Dealing with difficult situations
- Teamwork and communication; Supportive supervision
- Assertiveness; problem solving and growth mindset
- Cultural humility & responsiveness; Compassion & dependability
- Resilience & recovery; Safety & stability; Collaboration & empowerment

As part of the PTBi work in Migori, providers were introduced to simulation training for the management of obstetric and neonatal emergencies as well as teamwork and communication. We are thus working with PRONTO international to integrate new content into their curriculum that addresses the above issues. This will lead to the development of an integrated curriculum that will improve quality of care by addressing the key drivers of poor person-centered care as well as the technical aspects of care. We anticipate an initial large group training (about 20 providers per group) in a one- or two-day training followed by monthly updates provided through smaller groups such as the peer support groups.

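### Explicit SES bias is scored as a separate absolute sum for each vignette, so the plan never estimates the low-versus-high SES gap; the stated 0–27 range also does not fit eight four-point items

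*Combined protocol and SAP*

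**What the plan says.** The explicit bias score is one of four secondary outcomes in the SAP (Secondary outcomes; Box 2). The instrument is paired: "One vignette describes a woman with low SES and the other vignette a high SES woman". Administration and items are the same for both: "vignettes were read in counter-balanced orders to providers and followed by 8-questions". On responses, Box 2 says "Response options range from strongly disagree to strongly agree on a 4-point scale". On scoring, it says "Summative scores are created after recoding all responses to the same direction", and then "higher scores indicate higher bias towards the woman in the vignette. Scores range from 0 to 27".

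Box 2 gives no rule for combining the two vignette scores and defines no difference between them. Internal consistency is printed per vignette, "0.70 for the low SES vignette and 0.80 for the high SES vignette". Those figures stand in the IAT row of Box 2, which carries a description of the vignettes, and they are said to come from the study sample at baseline.

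The SAP section on secondary outcomes applies descriptive statistics, a paired Wilcoxon test within each group, and a difference in differences over time and group.

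The protocol's Justification for the study gives the construct: "Bias is the negative evaluation of one group relative to another". The training topics in protocol Table 1 include unconscious bias and also "Person-centered maternity care".

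**The concern.** The construct is relative, the instrument collects the two ratings needed for a relative measure, and the scoring does not use the comparison. A provider who rates both women equally poorly gets a high bias score with no SES difference at all. For example, on a 0–24 scale, a provider scoring 18 for each woman looks more biased than one scoring 14 (low SES) and 6 (high SES), although the gaps are 0 and 8.

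The vignette items cover matters such as introductions, consent, companionship and explanations. Training in person-centered care could shift answers about any woman, whatever her SES. Only the intervention group is trained, so subtracting the control group's change would not remove that shift. At stake is whether this outcome can distinguish a provider who treats low- and high-SES women more alike from one whose attitudes to all women have improved. The SAP intends the pilot's effect sizes to inform a larger trial, so an effect with an ambiguous label could carry forward.

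**Working it through.** **1. The stated range.** Inputs from Box 2: 8 items, 4 response points, summed. The numeric coding is not given.
- Coded 0–3: 8 × 0 = 0 to 8 × 3 = 24.
- Coded 1–4: 8 × 1 = 8 to 8 × 4 = 32.
- A maximum of 27 with a minimum of 0 needs 27 / 3 = 9 items coded 0–3.

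The plan's 0–27 is not reproduced under either coding. A low-minus-high difference would run from 0 − 24 = −24 to 24 − 0 = +24 (or 8 − 32 to 32 − 8, the same). The stated non-negative range therefore cannot describe a difference score.

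**2. What the planned estimator picks up.** The SAP's effect is (T2i − T1i) − (T2c − T1c). Let L and H be the low- and high-SES vignette scores, and suppose training shifts both by c beyond any control change. Then:
- effect on L = c
- effect on H = c
- effect on L − H = c − c = 0

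This needs no assumption about standard deviations or correlations. With assumed baseline means L = 14 and H = 10 (gap 4):

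| Assumed shift relative to control | Effect on L | Effect on H | Effect on mean of L and H | Effect on L − H | Gap after |
|---|---|---|---|---|---|
| Both fall by 2 | −2 | −2 | −2 | 0 | 4 |
| L falls by 1, H rises by 1 | −1 | +1 | 0 | −2 | 2 |
| H rises by 2, L unchanged | 0 | +2 | +1 | −2 | 2 |

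Row 1 is the main problem. Row 2 is hidden only if the two scores are pooled. Row 3 shows why the difference should not be reported alone: the gap narrows because ratings of the high-SES woman get worse.

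**3. How often a common shift would look like an effect.** Simulation with 40 per group, a common shift of 0.5 SD, no change in the gap, a two-sided 5% t-test on change scores and 4,000 runs. Assumed: pre-post correlation 0.3, 0.5 or 0.7; between-vignette correlation 0.3 or 0.6; no clustering by facility. The low-SES score was significant in about 47%, 59% and 81% of runs at the three pre-post correlations. The difference was significant in about 4.5% to 5.4%, which is the nominal level. These rates depend on the assumed shift and correlations; the algebra in step 2 does not.

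**4. Reliability of the difference.** With equal variances, reliability = (mean alpha − r) / (1 − r), where r is the between-vignette correlation. Mean alpha = (0.70 + 0.80) / 2 = 0.75.
- r = 0.3: 0.45 / 0.70 = 0.64
- r = 0.5: 0.25 / 0.50 = 0.50

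The documents do not give r, so both values are assumptions.

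**The case against.** The strongest reply is that the plan leaves the contrast out but does not exclude it. If both vignette scores are tabulated, the estimate can be recovered: with complete data, the difference in differences for L minus that for H equals the one for L − H. A reader would see −2 and −2 and could work out 0. That stands for the point estimate. It does not supply a confidence interval, which needs the covariance of the two scores within providers. The plan also does not say that both scores will be shown: it lists a single explicit bias score without saying whether the two are kept apart, summed or averaged.

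Other parts of the reply also stand:
- That training would move both scores is inferred from the list of topics. Several items ask about the woman's expectations, cooperation or pain, and no document shows a common shift.
- The low-SES score has its own value for a study concerned with the care of marginalized women.
- The SAP says the pilot is probably not powered for formal testing, so the significance rates in step 3 are illustrative.
- Because baseline alphas are already reported, redefining the outcome is a change made after baseline data were examined, not a mere wording edit.

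A reader might infer that the trial will report reduced SES bias when there is none. The documents do not support that: Box 2 ties its label to the woman in each vignette, and the analysis sections set no rule for drawing a conclusion about SES. A reader might also infer that a narrowing from opposite movements would go unseen. That follows only if the scores are pooled, which the plan does not state.

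**Conclusion.** The concern holds in a limited form. As written, the plan measures explicit SES bias with a paired instrument, scores each vignette in absolute terms, and provides no estimate or confidence interval for the gap between them. A common shift of c points appears as c on each score and 0 on the gap, so an equal fall could be read as reduced bias. The algebra is exact; that such a shift will occur is plausible but not shown, and its size is unknown.

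This is a secondary outcome in an 80-provider pilot. The matter is one of definition and labelling, and it does not threaten the primary outcomes. The range discrepancy is certain, but it is a separate documentation point that holds whichever scoring is chosen, and it adds no weight to the argument about the contrast.

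**What to change.** - In Box 2, add the within-provider low-minus-high vignette difference at each time point as the measure of explicit SES bias. State the item coding, and that items are recoded identically for both vignettes.
- Analyse that difference by the same difference in differences as the other secondary outcomes, with a confidence interval.
- Report both single-vignette scores beside it, so that a narrowing caused by worse ratings of the high-SES woman is visible and the low-SES score is kept.
- Date the change and state that it follows an examination of baseline data.
- Separately, reconcile the 0–27 range with the item count: 0–24 if coded 0–3, 8–32 if coded 1–4, and −24 to +24 for the difference.

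The cost is one derived variable from data already planned, plus SAP text. The real downside is reliability: about 0.64 to 0.50 for the difference under the assumed correlations, against 0.70 and 0.80 for the single vignettes. The contrast should therefore be presented as an estimate with its interval, not as a test.
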